## EQ-5D

Create flag for the country to be used to derive EQ-5D-3L (Country code - site ID: AU - 401, 402; GB - 403; FR - 404; SE - 406).

## Statistical Analysis Plan

A Multi-center Outcomes Clinical Study of the PyroTITAN™ HRA Shoulder Implant in Humeral Head Resurfacing

Number: CP-HRA-002  
ST: ST1159  
Version: 1.0 05/Oct/2023  
Page: 12 of 19

The individual dimension responses on a scale of 1-3 will be combined in the order: Mobility, Self-Care, Usual Activities, Pain/ Discomfort, Anxiety/ Depression to form a 5-digit EQ-5D-3L profile in the form XXXXX (where X is 1-3) describing the respondent's health state.

An EQ-5D-3L index value will be derived per subject by matching the 5-digit profile to the correct country and index value on the vendor supplied "EQ-5D-3L Crosswalk Index Value Calculator" [4].

Change from baseline (Pre-Operative visit) to each post-baseline visit in EQ-5D-3L index value will be derived as:

$$\text{Index value}_{\text{visit } n} - \text{Index value}_{\text{visit } 1}, \text{ where } n = 1,2,3 \dots, 10$$

Separate dimension responses should be derived using LOCF values as specified in section 7.3. These values should be used to calculate an LOCF version of the EQ-5D-3L Index value as above. The change from baseline in this value would then also be calculated in the same way as above.

### EQ VAS

Change from baseline to each post-baseline visit in EQ VAS score will be derived as:

$$\text{EQ VAS}_{\text{visit } n} - \text{EQ VAS}_{\text{visit } 1}, \text{ where } n = 1,2,3 \dots, 10$$

An LOCF version of EQ VAS should be calculated as specified in section 7.3. The change from baseline for this variable will also be calculated as above.

### Adverse events

Adverse events are recorded by the Investigator and then reviewed by the Adverse Events Monitoring Board (AEMB) at Smith + Nephew and documented in RAVE. The most stringent classification will be presented and reported. Investigator assessments will be provided in listings.

Investigators do not classify events, S+N use the Investigator assessment to classify the event as follows:

- An event will be classified as "related" if the relationship if rated as possible/probable/definite to the Device and/or procedure from the investigator assessment, otherwise it will be classified as "not related".
- An event will be classified as an ADE if the event is related to the study device and/or procedure.
- An event will be classified as an SAE if the event is serious.
- An event will be classified as an SADE if it is an ADE which is also serious.
- An event will be classified as a USADE if it is an SADE which is also unanticipated.
- Otherwise, the event will be a non-device, non-procedure related, non-serious AE.

For adverse events that have been resolved, duration of adverse event is calculated as end date minus start date.

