## **9.0 Adverse Events**

---

For the purpose of this study, an adverse event is defined as any medical condition or event for which the subject seeks medical attention that, in the physician’s opinion has an association with the medical device or operative procedure. Adverse events may be mild, moderate or severe. All adverse events, device related or procedure related, are transcribed from source documentation onto an Adverse Event CRF and forwarded to the Sponsor (one Adverse Event per CRF).

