### **9.5 Adverse Event Reporting:**

Investigators and /or study staff are required to report AEs (and all reportable effects) per their Institutional Review Board/Ethics Committee Standard Operating Procedures.

In the event of a complication, the Investigator and/or other professional personnel in attendance will undertake the appropriate therapy. All adverse signs and symptoms (device or procedure related) that occur during the study are to be recorded on an Adverse Event CRF. The description of adverse events will include cause, date of initial onset, severity, treatment, and date of resolution.

All serious and non-serious device or procedure related adverse events and unanticipated serious adverse device effects that occur during this investigation must be reported in a timely manner by the Investigator using either telephone or fax to:

ATTN: Clinical Research  
Ascension Orthopedics, Inc

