# Statistical Analysis Plan

A Multi-center Outcomes Clinical Study of the PyroTITAN™ HRA Shoulder Implant in Humeral Head Resurfacing

Number: CP-HRA-002  
ST: ST1159  
Version: 1.0 05/Oct/2023  
Page: 13 of 19

Due to system updates, checks need to be performed to ensure the most stringent classification is being reported. When comparing Investigator assessments (classifications as above) with AEMB classifications, the most stringent classification should be reported as follows:

Investigator assessment	AEMB classification	Most stringent
AE	SAE	SAE
SAE	AE	SAE
AE	ADE	ADE
ADE	AE	ADE
ADE	SADE	SADE
SADE	ADE	SADE
SAE	SADE	SADE
SADE	SAE	SADE
SADE	USADE	USADE
USADE	SADE	USADE

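### SAP 7.4 counts an event with a missing relationship rating as not related, so it drops out of the investigator-derived ADE, SADE and USADE summary in SAP 7.12, and only sponsor review can restore it

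*SAP*

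**What the plan says.** **Classification rule (SAP 7.4, Adverse events).** The sponsor derives a class from the investigator's assessment. An event is related if its relationship is rated possible, probable or definite "from the investigator assessment, otherwise it will be classified as 'not related". The device classes build on that flag: "An event will be classified as an ADE if the event is related to the study device and/or procedure". SADE adds seriousness, and USADE adds that the event was unanticipated. An event that is neither related nor serious falls to the last line: "Otherwise, the event will be a non-device, non-procedure related, non-serious AE".

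**Second review (SAP 7.4).** The AEMB at the sponsor reviews the recorded events. The more stringent of the investigator-derived and AEMB classes is to be reported, following a table of paired classes. The table is introduced with: "Due to system updates, checks need to be performed to ensure the most stringent classification is being reported".

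**Reporting (SAP 7.12).** The summary by class uses the investigator-derived class. Where the sponsor disagrees, its classes go into a separate summary.

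**Missing data (SAP 7.3).** Data are analysed as observed. Nothing is said about a missing relationship rating.

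**Protocol.** Section 9.0 limits adverse events to those that "in the physician’s opinion has an association with the medical device or operative procedure". Section 9.5 sets out the content of the record: "The description of adverse events will include cause, date of initial onset, severity, treatment, and date of resolution". Cause is on that list; a graded relationship scale is not named.

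**The concern.** A missing rating is not evidence that an event was unrelated. Under the protocol's definition, entering the event as an adverse event already implies that the physician saw an association. The SAP's default therefore gives such an event the class furthest from the reason it was recorded.

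ADE, SADE and USADE all require the related flag, so the default can only lower the investigator-derived counts. Adverse events are the safety endpoint of this study, and it has no control arm against which under-counting would show. A gap in the rating is conceivable: the protocol dates from May 2013 and the SAP from October 2023, and of the two documents only the SAP mentions the possible/probable/definite scale.

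**Working it through.** The plan gives no figure to reproduce, so the check traces an unrated event through the rules.

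**Step 1: investigator-derived class (SAP 7.4).** With no rating the event is 'not related'. It becomes an AE if non-serious and an SAE if serious. Whether it was unanticipated no longer matters, because USADE requires SADE.

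**Step 2: what is reported.** The table assumes that the AEMB agrees with the investigator on seriousness.

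| Unrated event | Investigator-derived class (7.12 main summary) | AEMB class if it finds the event related | 7.4 table gives | If AEMB also finds it not related |
|---|---|---|---|---|
| Non-serious | AE | ADE | ADE | AE |
| Serious, anticipated | SAE | SADE | SADE | SAE |
| Serious, unanticipated | SAE | USADE | pair not listed | SAE |

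In the third row only the general most-stringent sentence in 7.4 leads to USADE.

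**Step 3: completeness of the reconciliation table.** Five classes give 5 × 4 = 20 ordered discordant pairs. The table lists 10, so 20 − 10 = 10 are absent. They are these five combinations, each in both orders: AE/SADE, AE/USADE, SAE/ADE, SAE/USADE and ADE/USADE.

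**Step 4: which class is counted.** Section 7.4 says the most stringent class is presented and reported, with investigator assessments in listings. Section 7.12 says the summary uses the investigator-derived class. Under 7.12 an unrated event stays out of the main ADE/SADE/USADE counts whatever the AEMB decides. Under 7.4 it is left out only if the AEMB also does not call it related. The two sections conflict.

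**Step 5: size, as an illustration only.** Take 100 events, all associated in the sense of protocol 9.0. Let *b* be the share with no rating and *q* the share of those that the AEMB calls related. Both are assumptions; the documents give neither.

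- Investigator-derived count (7.12) = 100 × (1 − *b*)
- Most-stringent count (7.4, with its general rule covering unlisted pairs) = 100 × (1 − *b*) + 100 × *b* × *q*

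| *b* | 7.12 count | 7.4 count, *q* = 0 | 7.4 count, *q* = 0.5 | 7.4 count, *q* = 1 |
|---|---|---|---|---|
| 2% | 98 | 98 | 99 | 100 |
| 5% | 95 | 95 | 97.5 | 100 |
| 10% | 90 | 90 | 95 | 100 |

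The shortfall in the 7.12 count equals *b* by construction. The illustration shows direction and mechanism, not a predicted size.

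**The case against.** The strongest reply is that the plan has a safeguard. The AEMB reviews the events, and the 7.4 table raises AE/ADE to ADE and SAE/SADE to SADE, which are the usual pairs when a missing rating has lowered the investigator-derived class. This stands. A reader might infer that unrated events are lost from every device-effect count; the documents do not support that. Loss is certain only in the investigator-derived summary of 7.12, and an event the AEMB upgrades would still appear in the separate sponsor summary.

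Second, nothing shows that ratings are missing. The case report forms are not in the text, the protocol's list of record content need not be complete, and 'otherwise' may simply have been meant for the remaining answers on the scale. The protocol makes the investigator responsible for complete forms (14.2), bars delegation of the adverse event form signature (17.0) and has monitors check completeness (19.2). SAP 7.12 also lists relationship to device and to procedure for each event, so gaps should be visible. This stands too: the frequency is unknown. The remark about system updates explains why the two classifications are compared; it is not evidence of blank fields. Likewise, the most-stringent principle governs that comparison and is not a rule for missing values.

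Third, if protocol 9.0 makes every recorded event an associated one, an explicit 'not related' rating looks equally inconsistent. That goes too far. Protocol 7.0 treats every later operation on the shoulder as an adverse event, and 16.0 has deaths documented on the Adverse Event/Withdrawal form, so some entries need not imply an association. An explicit rating is information; a missing one is not.

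Finally, the primary endpoint is not at issue. SAP 7.4 derives it from removals or revisions, complication forms and adverse events, not from the ADE class.

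**Conclusion.** The point holds as a defect in the rule, of unknown and possibly zero size. SAP 7.4 has no provision for a missing relationship rating, and read literally its residual class makes such an event 'not related', against the protocol's definition of an adverse event. The event then drops out of the main ADE/SADE/USADE summary under 7.12. It also drops out of the most-stringent count under 7.4 unless the AEMB calls it related. For a serious, unanticipated event, the table lacks the pair needed to restore it.

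The default can only lower the counts. This conclusion rests on a literal reading of 'otherwise' and on the event having been entered under the protocol 9.0 definition. The shares of 2%, 5% and 10% are assumptions and say nothing about the actual data. If every event has a rating, the default changes no count; the conflict between 7.4 and 7.12 and the gaps in the table remain.

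**What to change.** In SAP 7.4:

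- Class an event as 'not related' only when the investigator gave an explicit rating other than possible, probable or definite for both device and procedure.
- Query missing or unknown ratings with the site. Treat those still unresolved at analysis as related, and footnote the number classified this way.
- Add the missing pairs, SAE/USADE among them, to the reconciliation table.

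In SAP 7.12, state that the most-stringent class from 7.4 is the one tabulated.

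The cost is a few sentences, some added table rows, a small programming change and any site queries. Treating unresolved ratings as related is a convention, and a conservative one: it may raise the ADE count slightly, and the footnote lets the reader see by how many events.

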# Statistical Analysis Plan

A Multi-center Outcomes Clinical Study of the PyroTITAN™ HRA Shoulder Implant in Humeral Head Resurfacing

Number: CP-HRA-002  
ST: ST1159  
Version: 1.0 05/Oct/2023  
Page: 13 of 19

Due to system updates, checks need to be performed to ensure the most stringent classification is being reported. When comparing Investigator assessments (classifications as above) with AEMB classifications, the most stringent classification should be reported as follows:

Investigator assessment	AEMB classification	Most stringent
AE	SAE	SAE
SAE	AE	SAE
AE	ADE	ADE
ADE	AE	ADE
ADE	SADE	SADE
SADE	ADE	SADE
SAE	SADE	SADE
SADE	SAE	SADE
SADE	USADE	USADE
USADE	SADE	USADE

## 7.5 Baseline Data

The following data is to be summarised at baseline. If any baseline data is to be summarised together with later visit data then the analysis will be described in the relevant endpoint section and not in this section.

### Screening

- Baseline demographics: age (years); gender and dominant side
- Baseline Vital Signs: height (cm); weight (kg); BMI(kg/m^2)
- Medical history/ Primary Diagnosis/ Presenting symptoms
- Concomitant Medications/ Medical Conditions

### Operative Details

- Surgical details (Operative side, operative time, estimate blood loss, patient transfusion, bone grafting, cement use, stability upon implantation)
- Walch Classification
- Glenoid reshaping
- Surgical approach
- Treatment of Bicep tendon
- Intraoperative complications
- Time to discharge

## Statistical Analysis Plan

A Multi-center Outcomes Clinical Study of the PyroTITAN™ HRA Shoulder Implant in Humeral Head Resurfacing

Number: CP-HRA-002  
ST: ST1159  
Version: 1.0 05/Oct/2023  
Page: 14 of 19

### 7.6 Disposition Data

- The number of subjects screened.
- The number of subjects attending each study visit will be summarised with the dates of first subject first visit and last subject last visit inserted into the footnote.
- Reason for study completion

### 7.7 Protocol Deviations

The frequency of protocol deviations will be summarized along with the number of subjects experiencing each.

### 7.8 Multiplicity

No adjustments for multiplicity are planned for this study.

### 7.9 Analysis of Primary Endpoint(s)

A composite endpoint for Clinical success (device survival) is defined as a binary variable (1/0) (1 if all the following are true and 0 if any is false):

- A. Device remains implanted.
- B. Absence of device-related complications requiring surgical replacement, removal, or augmentation of components.
- C. Freedom from chronic dislocation.

The primary endpoint is the clinical success (device survival) rate at 10-years.

The study hypothesis is to test whether the 10-year survival (i.e., clinical success) rate in the investigational PyroTITAN HRA group is non-inferior to the reference rate at 96.1%. This study will be considered successful if the upper bound of the two-sided 95% confidence interval for the success rate difference (reference – study survival rate) is less than the non-inferiority margin of 3.3%.

The primary non-inferiority hypothesis is formulated as:

$$H_0: P_0 - \delta \geq P_T$$

$$H_a: P_0 - \delta < P_T$$

The variables are defined as follows:

$P_T$  = 120-month success rate in the PyroTitan HRA group

$P_0$  = Reference success rate from original population

$H_0$  = Null hypothesis

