**Confidential**

Protocol Date: May 27, 2013

Amendment 1

Revision 2

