## **11.3 Sample Size and Power Analysis**

The original sample size in this study was 150 enrolled subjects. Additional proof testing and improvements in the device inspection process were employed during the study, at which time it was determined that an additional cohort of subjects was necessary. We are now comparing a cohort of subjects enrolled after these changes to the original cohort of subjects.

With an expected attrition rate of 10% per annum, this will yield an evaluable sample size of 52 shoulders at ten years ( $150 * 0.9^{10} = 52.3$ , where 0.9 or 90% is the number expected to be retained from one year to the next). Based on past experience, we may obtain clinical follow-up on this number of shoulders, but we may obtain radiographic follow-up on as few as two-thirds of these shoulders (about 35 shoulders). This remaining number of evaluable shoulders with clinical and radiographic follow-up is adequate to establish a reliable ten-year survival estimate of survival for hemi arthroplasty (Dorey and Amstutz, 1986).

For the new cohort, the sample size is calculated based on the non-inferiority of the study device. The success rate for the study device is 96.1% from the original population and is used as reference rate. Therefore, for a conservative success rate of 96.1% of the study device is used in the study. The non-inferiority margin  $\delta$  of -0.033 is chosen in the study. 212 subjects are required to achieve  $100(1 - \beta) \% = 80\%$  power to detect non-inferiority at the Significance level of  $\alpha = 0.05$ . To account for 10% lost to follow-up, the

total number of additional subjects is 237. Therefore, the estimated enrollment for the study will be 387 subjects.

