**Ascension Orthopedics**

CP-HRA-002

of anesthesia (general, epidural, spinal). Separate consent forms will be presented to subjects outlining the risks of shoulder surgery and anesthesia. In addition to these there are risks associated with a surgical procedure that involves a device, including the following: damage to nervous and vascular tissue, infection, long term swelling, fracture of bone surrounding the device, loosening, dislocation or fracture of the device, hemorrhage, decrease in range of motion or mobility deformity, allergic reaction to the device and failure of the device to be incorporated into the body. A complication may require revision surgery. Very rarely a complication may prove fatal. This clinical trial of the CE marked (November 30th, 2009)PyroTITAN™ HRA Shoulder prosthesis, used according to this protocol and labeling indications, poses no additional risks over those normally associated with shoulder resurfacing arthroplasty.

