## **18.0 Record of Device Inventory**

---

This is a post market study and all devices are CE marked. Therefore inventory control is not a regulatory requirement.

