# 6 STATISTICAL CONSIDERATIONS

## 6.1 Determination of Sample Size

The following is the sample size justification taken from the study protocol V2, 27-May-2013:

The original sample size in this study was 150 enrolled subjects. Additional proof testing and improvements in the device inspection process were employed during the study, at which time it was determined that an additional cohort of subjects was necessary. We are now comparing a cohort of subjects enrolled after these changes to the original cohort of subjects.

With an expected attrition rate of 10% per annum, this will yield an evaluable sample size of 52 shoulders at ten years ( $150 * 0.9^{10} = 52.3$ , where 0.9 or 90% is the number expected to be retained from one year to the next). Based on past experience, we may obtain clinical follow-up on this number of shoulders, but we may obtain radiographic follow-up on as few as two-thirds of these shoulders (about 35 shoulders). This remaining number of evaluable shoulders with clinical and radiographic follow-up is adequate to establish a reliable ten-year survival estimate of survival for hemi arthroplasty (Dorey and Amstutz, 1986).

For the new cohort, the sample size is calculated based on the non-inferiority of the study device. The success rate for the study device is 96.1% from the original population and is used as reference rate. Therefore, for a conservative success rate of 96.1% of the study device is used in the study. The non-inferiority margin  $\delta$  of -0.033 is chosen in the study. 212 subjects are required to achieve  $100(1 - \beta) \% = 80\%$  power to detect non-inferiority at the Significance level of  $\alpha = 0.05$ . To account for 10% lost to follow-up, the total number of additional subjects is 237. Therefore, the estimated enrolment for the study will be 387 subjects.

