## Statistical Analysis Plan

A Multi-center Outcomes Clinical Study of the PyroTITAN™ HRA Shoulder Implant in Humeral Head Resurfacing

Number: CP-HRA-002  
ST: ST1159  
Version: 1.0 05/Oct/2023  
Page: 15 of 19

$H_a$  = Alternative hypothesis that the success rate in the investigational group is non-inferior to the reference rate

$\delta$  = Non-inferiority margin pre-specified to be 3.3%.

The survival rate (the clinical success rate) will be calculated and the associated 95% exact confidence interval presented. If the upper 95% confidence limit is greater than the reference rate minus the non-inferiority margin ( $96.1 - 3.3 = 92.8\%$ ) then non-inferiority of the observed rate to the reference rate to within a 3.3% margin can be concluded.

Additionally, survival rate (the clinical success rate) and the associated 95% exact confidence interval at 2 and 5 years will be calculated and presented.

If data allows, time-to-event curves for device survival will be estimated using the Kaplan-Meier technique. For analysis of device survival, those lost to follow up or withdrawn from the study for reasons other than device revision or removal will be regarded as censored observations.

The primary analysis of this endpoint is to be carried out using the FAS population. The same analysis will be carried out on the PP population as supporting analyses.

As an additional analysis, the primary endpoint will be summarised for PP1 and PP2 populations in order to compare the cohort of subjects enrolled after the device changes to the original cohort of subjects.

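### SAP 7.9 tests the 10-year success rate against a 96.1% reference that has no stated time point and can rest on at most about 3.5 years of follow-up, so the stated 80% power does not describe the 10-year test.

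*SAP*

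**What the plan says.** SAP 7.9 gives the study hypothesis as to "test whether the 10-year survival (i.e., clinical success) rate in the investigational PyroTITAN HRA group is non-inferior to the reference rate at 96.1" per cent. It defines the tested quantity as the success rate at 120 months and the reference as the rate in the original population. The margin is given as "Non-inferiority margin pre-specified to be 3.3" percentage points, so the threshold is 96.1 − 3.3 = 92.8%.

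The reference comes from Protocol 11.3: "The success rate for the study device is 96.1% from the original population and is used as reference rate". The same figure is the assumed true rate in the sizing: "for a conservative success rate of 96.1% of the study device is used in the study". SAP 6.1 repeats this text from the 2013 protocol, including "212 subjects are required to achieve" 80% power. Neither document says at what follow-up time 96.1% was observed.

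Three other statements bound that time:

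- The protocol carrying the figure is headed "Protocol Date: May 27, 2013".
- Protocol 12.0 dates the CE mark: "This clinical trial of the CE marked (November 30 th , 2009").
- Protocol 18.0 says "This is a post market study and all devices are CE marked".

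**The concern.** Success requires the device to stay in place, with no device-related complication requiring replacement, removal or augmentation of components, and no chronic dislocation. Each failure is permanent, so the success rate can only fall as follow-up lengthens. A rate observed in the first few years is not a benchmark for year 10 unless something is added for later failures, and neither document adds anything.

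Two things are at stake. The first is the study's only formal success criterion: a cohort as durable as the original one could fall short of 92.8% at 10 years merely because it was watched for longer. The second is the power statement. It takes the true rate to be 96.1%, which at 120 months amounts to assuming that the early rate does not decline at all.

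**Working it through.** **Follow-up behind the reference.** The CE mark is dated 30 November 2009 and the protocol 27 May 2013. The difference is 1,274 days, and 1,274 / 365.25 = 3.49 years. No subject implanted after the CE mark could have had longer follow-up when 96.1% was written down. Protocol 5.1 planned the initial accrual over twelve months, so typical follow-up would have been shorter.

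**Reproducing the plan's figure.** One-sample non-inferiority against a fixed rate, normal approximation, one-sided 5%:

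n = P(1 − P)(z₀.₉₅ + z₀.₈₀)² / δ² = 0.961 × 0.039 × (1.645 + 0.842)² / 0.033² = 212.8.

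The plan states 212. Power at 212 is

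Φ[(P − 0.928) / √(P(1 − P)/212) − 1.645].

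At P = 0.961 this is Φ(0.033 / 0.01330 − 1.645) = Φ(0.837) = 79.9%. This identifies the sizing model. One-sided 2.5% would give 271, and a two-sample comparison 426 per arm, so neither is what was used.

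**Adding late failures.** Keep that model, and let a share f of the implants surviving at the reference time fail by year 10. Then P = 0.961 × (1 − f).

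| f | 10-year rate | Power, n = 212 |
|---|---|---|
| 0 | 96.1% | 79.9% |
| 0.5% | 95.6% | 64% |
| 1% | 95.1% | 48% |
| 2% | 94.2% | 22% |
| 3% | 93.2% | 8% |

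**Two assumed hazard shapes.** The documents give no failure times, so both shapes are assumptions. Let H = −ln(0.961) = 0.0398 be the cumulative hazard at time T, and S(10) = exp[−H(10/T)^k].

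- Constant hazard (k = 1), T = 3.49 years: S(10) = exp(−0.0398 × 10/3.49) = 89.2%. This is below 92.8%, and power is 0.04%.
- Strongly falling hazard (Weibull, k = 0.5), T = 3.49 years: S(10) = exp(−0.0398 × √(10/3.49)) = 93.5%. Power is 11%.
- If 96.1% were a 2-year rate, the same formulas give 82.0% (power about 0) and 91.5% (power 1%).

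**Dependence on the analysis set and interval.** The figures above use the sizing model. SAP 7.9 runs the primary analysis on the FAS (387 planned) and specifies an exact two-sided 95% interval.

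- All 387 evaluable, normal approximation, one-sided 5%: power is 80% at a true rate of 95.4%, so about 0.7 points of late failure are tolerated.
- Exact two-sided 95% interval with lower limit above 92.8% and no late failure: power is 41% at 212 (at least 205 successes needed) and 74% at 387 (at least 370 needed).
- The protocol's own attrition of 10% a year would leave 387 × 0.9¹⁰ = 135 subjects at year 10, so 387 evaluable is optimistic.

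**The case against.** The case against has real content.

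- **Zero late failures.** A reader might infer that the 80% holds if, and only if, no implant fails after the reference was measured. The documents do not support that as a general statement. It describes 212 subjects, a normal one-sided 5% test and an early rate of exactly 96.1%. A larger evaluable FAS tolerates some late failure under that test, and a better early rate in the new cohort, after the added proof testing and inspection, would absorb some too. With the exact interval, zero late failure does not reach 80% at all.
- **A near-certain miss.** A reader might infer that an equally durable device will normally fail the test. That depends on the hazard shape and on which of two conflicting rules in SAP 7.9 is applied. The section first requires the upper bound of the difference (reference minus study) to be below 3.3%, which means a lower limit of the study rate above 92.8%. It later accepts an upper limit above 92.8%. Under that second rule, a true rate of 89.2% would pass about 56% of the time at n = 212. The conflict is a separate error, and it would partly hide this one.
- **Misreading as inferiority to the original cohort.** The primary test pools both cohorts, and SAP 7.9 already plans a PP1 and PP2 summary and rates at 2 and 5 years. A failed test would not in itself be a comparison of new with original.
- **Status and direction.** The protocol calls the study exploratory, and neither document ties the 80% expressly to 120 months. Under the lower-limit rule the mismatch makes success harder and does not create false claims of success.

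These points narrow the size of the effect. None supplies a time point for 96.1% or an allowance for later failures, and SAP 7.9 nonetheless makes this comparison the criterion for study success.

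**Conclusion.** The mismatch of time horizons holds. A cumulative 120-month rate is tested against a figure that rests on at most about 3.5 years of follow-up. The 80% power, reproduced at 79.9%, belongs to a true rate of 96.1% at whatever time that was measured, and does not carry over to year 10. Under the sizing's own model, 0.5% to 2% late failure takes power to between 64% and 22%. It is about 11% under the assumed Weibull shape and about 0 under the assumed constant hazard.

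This rests on three things: the 3.49-year cap, which is inferred from dates because no first-implant date is given; the plan's own early rate of 96.1%; and the rule in SAP 7.9 that requires the difference to be bounded below 3.3%. The hazard scenarios show a range and do not predict the outcome.

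**What to change.** In SAP 7.9:

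- State the follow-up time to which 96.1% refers.
- Apply the 96.1% minus 3.3% test at that same time. Use 24 months only if that is what 96.1% represents; nothing in the documents says so.
- Report the 10-year rate with its confidence interval and without the 92.8% threshold.

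In SAP 6.1, say that the 80% refers to a rate at the reference's follow-up time and not at 120 months. Declare both changes in 7.14. Correct the conflicting upper-limit rule in 7.9 separately.

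Replacing the reference with the original cohort's own 120-month estimate is tempting. Subjects behind the 96.1% were implanted by 27 May 2013, so their last window (3,650 + 90 days) closed by 23 August 2023, before the SAP of 5 October 2023. That estimate can be shown with its interval as a descriptive PP1 versus PP2 comparison. It should not simply become the reference in a FAS test. Those subjects are part of the FAS, and Protocol 11.3 expects only about 52 of them to be evaluable at ten years. At 47 of 52, for illustration, the exact 95% interval runs from 79% to 97%, too wide for a 3.3-point margin.

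The cost is SAP wording, with no new subjects or visits. The downside is that the 10-year result loses its formal pass/fail threshold and the 80% label, and that the change comes late in an open study.
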